2. STUDY OBJECTIVES

Given that there is no one “gold-standard” way to characterize the efficacy of naloxegol to prevent lower GI tract paralysis in critically ill adults administered scheduled opioids, given the Phase II, proof of concept nature of this investigation we plan to consider multiple outcomes to evaluate naloxegol’s efficacy in this population. Since the original April 2015 protocol submission, in an effort to help better define those outcomes that are most relevant to clinicians when they are considering the efficacy (and safety) of a preventative strategy like naloxegol in their critically ill patients at risk for lower GI tract paralysis, we informally surveyed clinicians at Tufts Med Center (and elsewhere). Of note, time to the first spontaneous bowel movement (SBM) (which is directly related to our primary outcome of prevention of lower GI tract paralysis) was suggested most frequently as the most clinically relevant outcome when evaluating a new lower GI tract paralysis prevention intervention. Clinicians noted that once a patient receiving scheduled opioid therapy has their first SBM (and remained on any particular lower GI tract prophylaxis regimen) that the patient should ideally be expected to have a SBM at least daily. Therefore, these clinicians felt that comparing the ICU days without a SBM (noting that when 3 days without a SBM is met, the definition for lower GI tract paralysis is met) was also a clinically meaningful way to compare naloxegol with placebo. While most respondents questioned whether it was necessary (or even possible) to rigidly define a SBM (e.g., based on a specific fecal output volume), they suggested that we collect the following data for each SBM [1. Stool volume (i.e., small, medium or large) and 2. Stool consistency (i.e. using the Bliss stool scale score)] Clinicians generally felt that the other outcomes that were proposed in the previous version of this protocol (for both efficacy and safety) in April 2015 were all appropriate and should all be collected given the pilot nature of this investigation. With the recently published study by Palacio de Azeda et al [13] that found that the use of an aggressive daily lactulose and enema protocol reduced the average daily SOFA (organ severity) score, and that highlighted that there may be an important connection between lower GI tract paralysis and abdominal pressure, we would like to incorporate collection of daily SOFA scores and thrice daily measurement of abdominal pressure as an efficacy outcome in the study. Lastly, a recent paper found a strong relationship between delirium and lower GI tract paralysis in the critically ill and thus we propose to monitor each subject twice daily for delirium. [12].

Overall Study Aim

The overall aim of this Phase II, proof of concept study is to evaluate the efficacy and safety of naloxegol (versus placebo) in preventing lower GI tract paralysis in critically ill adults initiated on scheduled intravenous (IV) opioid therapy.

2. 1 Primary objective

The primary objective of this single-center, Phase II, proof of concept study in critically ill adults initiated on scheduled IV opioid therapy is to compare the incidence of lower GI tract paralysis [from the time of a study enrollment (i.e., randomization) to ICU discharge, death or 10 days of study drug administration (whichever comes first)] between naloxegol 25mg daily and placebo-treated groups.

Drug Substance: Movantik
 Study Number: ESR-15-11000
 Tufts IRB #12043
 Version: Protocol version #19
 Date: September 10, 2018

Note:

1. For the purposes of the study, any rectal output will be considered a SBM as long as it is not temporally related to the insertion of a rectal tube or the insertion of a suppository (as per the study laxative protocol (Appendix 1)).
2. Patients with preexisting lower GI tract paralysis are excluded from the study.
3. Patients not expected to survive their ICU stay are excluded from the study.

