3.1 Overall study design and study flow chart

Drug Substance: Movantik
Study Number: ESR-15-11000
Tufts IRB #12043
Version: Protocol version #19
Date: September 10, 2018

This will be a Phase II, proof of concept, single-center, randomized, double-blind, placebo-controlled pilot study to assess the efficacy and safety of naloxegol for preventing lower GI tract paralysis in 36 (18 naloxegol; 18 placebo) medical critically ill adults who require scheduled IV opioid therapy.

Drug Substance: Movantik
 Study Number: ESR-15-11000
 Tufts IRB #12043
 Version: Protocol version #19
 Date: September 10, 2018

Table 1. Study Plan

Study period	ICU admission and initiation of scheduled opioid	Treatment Period (maximum of 10 days)										Study drug stopped or early termination	Discharge from ICU	
		1	2	3	4	5	6	7	8	9	10			
Study day	Maximum of 72 hrs to enroll patient													
Screening	√													
Randomization		√												
Use of study laxative guideline		√	√	√	√	√	√	√	√	√	√			
Administration of study medication		√	√	√	√	√	√	√	√	√	√			
Baseline demographic information	√	√												
Inclusion/Exclusion criteria	√													
Pregnancy test for WOCBP	√													
Efficacy outcomes														
Monitoring that is a routine part of care at Tufts MC														
Bedside nurse														
Documentation of all SBMs	√	√	√	√	√	√	√	√	√	√	√			
Volume of enteral nutrition administered		√	√	√	√	√	√	√	√	√	√			
Fluid balance		√	√	√	√	√	√	√	√	√	√			
Sedation assessment SAS (q6h)		√	√	√	√	√	√	√	√	√	√			
Pain assessment (numerical rating q6h)	√	√	√	√	√	√	√	√	√	√	√			
Delirium assessment (ICSDC q12h)		√	√	√	√	√	√	√	√	√	√			
Investigative team														
Documentation of study laxative guideline use		√	√	√	√	√	√	√	√	√	√			
% of daily enteral nutrition goal achieved		√	√	√	√	√	√	√	√	√	√			
Daily opioid requirements	√	√	√	√	√	√	√	√	√	√	√			
Daily sedative requirements		√	√	√	√	√	√	√	√	√	√			

Drug Substance: Movantik
 Study Number: ESR-15-11000
 Tufts IRB #12043
 Version: Protocol version #19
 Date: September 10, 2018

Serum creatinine to calculate creatinine clearance	√	√	√	√	√	√	√	√	√	√	√	√	
Monitoring that is not a routine part of care at Tufts MC													
Bedside nurse													
Characterization of each SBM for size		√	√	√	√	√	√	√	√	√	√	√	
Characterization of each SBM using the Bliss Scale		√	√	√	√	√	√	√	√	√	√	√	

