5.8 Discontinuation of investigational product

5.8.1. Procedures for discontinuation of a subject from investigational product

Study drug administration will be stopped when one of the following occurs:

1. The subject experiences an adverse event potentially attributable to the study drug that is deemed, in the opinion of principal investigator, to warrant discontinuation of therapy.
2. The patient requires use of the Level 4 Study Laxative Guideline (i.e., methylnaltrexone)
3. Scheduled opioid therapy is stopped for ≥ 24 hours and the patient has had ≥ 1 SBM since the time of study enrollment.
4. The patient has been administered 10 days of study medication.
5. The patient is discharged from the ICU.
6. The patient dies in the ICU.
7. The patient requires a strong CYP3A4 inhibitor medication (and no other therapeutic alternative medication without this property can be used)
8. The patient develops excessive diarrhea defined as ≥ 3 SBMs with a Bliss Score of 3 or 4 in a 24 hour period. When excessive diarrhea first occurs, study medication will be held. In addition, all laxatives

Drug Substance: Movantik
 Study Number: ESR-15-11000
 Tufts IRB #12043
 Version: Protocol version #19
 Date: September 10, 2018

will be stopped (including docusate) and the investigative team will work with the subject's clinical team to identify other possible causes for the excessive diarrhea (e.g. enteral nutrition formulation choice, C. difficile infection etc). In a further 24 hours (48 hours after the last study medication dose), if excessive diarrhea persists, the study medication will be permanently discontinued. However, if the subject no longer has excessive diarrhea in a further 24 hours (48 hours after the last study medication dose), study medication will be resumed at the original dose. If excessive diarrhea occurs again after study medication is resumed, then the study medication will be permanently stopped.

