5.9 Withdrawal from study

While 5.8.1 lists the reasons why study drug administration will cease, post-study drug discontinuation outcomes like duration of ICU stay will still be collected.

Should consent for study participation be withdrawn all study data collection activities will cease and no study data collected before the time of withdrawal will be used.

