12.2 Methods of statistical analysis

Baseline characteristics of patients will be compared using standard univariate methods (chi-square test, t-test) to confirm the randomization was successful in achieving comparable groups. To test the primary outcome (incidence of lower GI tract paralysis), given that there may be censoring (i.e., subject may die or withdraw from study before developing lower GI tract paralysis), we will present Kaplan-Meier curves for the naloxegol and placebo groups for the time to first development of lower GI tract paralysis (≥ 3 days without a SBM after study randomization) during the ICU stay up to 10 days and compare the curves using a log-rank test. If all subjects complete the study (e.g., no deaths, no withdrawal or loss-to-follow-up for other reasons), then we will instead compare the proportion of patients that develop lower GI tract paralysis after study randomization during the ICU stay up to 10 days between the naloxegol and placebo groups using a chi-square test. The secondary outcome, time to first SBM will be estimated using a Kaplan Meier time to event analysis and compared between groups using a log-rank test. The secondary outcome of the number of ICU days without a SBM will be compared between the naloxegol and placebo groups using the Poisson regression for count data and adjusting for total number of days in the ICU (up to a maximum of 10) as an offset term in the Poisson model. The secondary outcome of the average daily opioid requirements will be compared between groups using either a student t-test or nonparametric Wilcoxon rank-sum test if the assumptions of the student t-test fail to be met. Length of mechanical ventilation and ICU stay will be reported as medians and interquartile ranges and will be compared using the Wilcoxon Rank Sum Test. For all statistical tests of hypotheses, a two-sided p-value of ≤ 0.05 will be considered as statistically significant. As this is a Phase II proof of concept study a p value of <0.10 may still be worth consideration for future study, however. All statistical analyses will be performed using SPSS 17.0. (SPSS, Chicago, IL) or other comparable commercially available statistical software.

[figure not shown]

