12.2 Methods of statistical analysis

[figure not shown]
Baseline characteristics of patients will be compared using standard univariate methods (chi-square test, t-test) to confirm the randomization was successful in achieving comparable groups. To test the primary outcome (incidence of lower GI tract paralysis), given that there may be censoring (i.e., subject may die or withdraw from study before developing lower GI tract paralysis), we will present Kaplan-Meier curves for the naloxegol and placebo groups for the time to first development of lower GI tract paralysis (≥ 3 days without a SBM after study randomization) during the ICU stay up to 10 days and compare the curves using a log-rank test. If all subjects complete the study (e.g., no deaths, no withdrawal or loss-to-follow-up for other reasons), then we will instead compare the proportion of patients that develop lower GI tract paralysis after study randomization during the ICU stay up to 10 days between the naloxegol and placebo groups using a chi-square test. The secondary outcome, time to first SBM will be estimated using a Kaplan Meier time to event analysis and compared between groups using a log-rank test. The secondary outcome of the number of ICU days without a SBM will be compared between the naloxegol and placebo groups using the Poisson regression for count data and adjusting for total number of days in the ICU (up to a maximum of 10) as an offset term in the Poisson model. The secondary outcome of the average daily opioid requirements will be compared between groups using either a student t-test or nonparametric Wilcoxon rank-sum test if the assumptions of the student t-test fail to be met. Length of mechanical ventilation and ICU stay will be reported as medians and interquartile ranges and will be compared using the Wilcoxon Rank Sum Test. For all statistical tests of hypotheses, a two-sided p-value of ≤ 0.05 will be considered as statistically significant. As this is a Phase II proof of concept study a p value of <0.10 may still be worth consideration for future study, however. All statistical analyses will be performed using SPSS 17.0. (SPSS, Chicago, IL) or other comparable commercially available statistical software.

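### The primary outcome has two different ends of follow-up, and it is not clear that bowel movements are recorded after study drug stops

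*Protocol*

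**What the plan says.** **End of follow-up.** Protocol 2.1 runs the primary outcome from randomization to "ICU discharge, death or 10 days of study drug administration (whichever comes first". Sections 2.2 and 2.3 use the same end for the secondary and safety outcomes. Section 12.2, in both protocol and SAP, defines the event as "≥ 3 days without a SBM after study randomization" and looks for it "during the ICU stay up to 10 days and compare the curves using a log-rank test". It does not mention study drug.

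**Censoring.** Section 12.2 gives as its reason for Kaplan-Meier that a "subject may die or withdraw from study before developing lower GI tract paralysis". A chi-square test replaces the log-rank test if all subjects complete the study. Neither passage says how a patient is handled whose drug stops early while still in the ICU.

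**Drug stopping.** Section 5.8.1 lists eight rules. Rule 3 applies when "Scheduled opioid therapy is stopped for ≥ 24 hours and the patient has had ≥ 1 SBM since the time of study enrollment". Rule 8 holds drug, and may stop it for good, after three or more loose SBMs in 24 hours.

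**Recording.** Table 1 (section 3.1) is headed "Treatment Period (maximum of 10 days". Its row for documentation of all SBMs is ticked before treatment and on days 1 to 10 only. Section 5.9 says that "post-study drug discontinuation outcomes like duration of ICU stay will still be collected" and does not name SBMs.

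**The concern.** The event is any 3-day gap without an SBM, not only a late first one. A patient can have one SBM, come off opioid, meet rule 3 and then pass no stool for three days in the ICU. Section 12.2 counts that as an event, but it is seen only if someone is still recording.

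If follow-up ends with drug, patients leave observation partly because they have had an SBM, and more of them leave in the arm where SBMs come earlier. The log-rank test assumes that censoring is unrelated to the event. With 18 patients per arm, a few patients handled differently could change the result, and the choice would be made after the data are in.

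**Working it through.** **1. The plan's own power figure.** It assumes complete follow-up. Take hazards from the day-4 rates of failing to defecate (90% vs 40%), 18 per arm and 10 days of follow-up.
- Hazard ratio = ln(0.40)/ln(0.90) = 8.70.
- First-SBM events = 18 × (1 − 0.90^2.5) + 18 × (1 − 0.40^2.5) = 4.2 + 16.2 ≈ 20.3.
- Power = Φ(√20.3 × ln(8.70)/2 − 1.96) = 99.8%, as stated.
- With only 4 days of follow-up the same formula gives 97.0%. The stated figure therefore matches full 10-day follow-up.

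**2. The two windows side by side, for a patient who stays in the ICU.**

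| Case | 2.1 | 12.2 |
|---|---|---|
| Ten daily doses, no interruption | day 10 | day 10 |
| One dose held under rule 8, then resumed 48 h after the last dose | ten doses take at least 11 days; Table 1 has no day 11 | day 10 |
| Drug stopped for good on day 3 | ten drug days are never reached, so read literally there is no cap before ICU discharge or death | day 10 |

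**3. Recording after drug stops.** Table 1 has a column for study drug stopped or early termination. The row for documentation of all SBMs has no tick there. The rows for SBM size and Bliss score carry 11 ticks starting at day 1, so they appear to reach it. The rows disagree, though column alignment in the extracted table is uncertain. ICU stay in 5.9 is only an example.

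**4. Size if follow-up ended at rule 3.** This is a simulation of 20,000 patients per arm.
- From the plan's power table: 80% (placebo) vs 40% (naloxegol) without an SBM at day 4. First-SBM hazard = −ln(S)/96 per hour, which is 0.0023 and 0.0095.
- Assumed, because the documents give no rates: later SBMs every 36-48 h on average; opioid stopped after a mean of 48-120 h; ICU stay of 48 h plus a mean of 144 h.
- Drug stop = the later of (opioid stop + 24 h) and first SBM. Event = first 72-h gap within 240 h in the ICU.

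Results:
- Cut off event-free while still in the ICU: about 27-41% on naloxegol and 7-12% on placebo. Of 18 per arm, that is about 5-7 patients (0.27 × 18 = 4.9; 0.41 × 18 = 7.4) against 1-2 (0.07 × 18 = 1.3; 0.12 × 18 = 2.2).
- Crude proportions, counting these patients as event-free: the difference is exaggerated by about 6-11 points. For example, 78% vs 62% (16 points) becomes 73.5% vs 47% (26.5 points).
- Kaplan-Meier, censoring them at drug stop: the naloxegol estimate rises, for example from 0.78 to 0.87, and the difference shrinks, for example from 14.6 to 7.8 points. Log-rank power at 18 per arm falls from about 44-46% to 26-41%.

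**5. Cross-check with other assumptions.** Here 90% vs 40% at day 4, no ICU discharge, 10 days. Differences are placebo minus naloxegol.

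| Later SBMs/day | Opioid-stop hazard/day | Full follow-up | Crude, cut at stop | Kaplan-Meier, cut at stop | Log-rank power, full → cut |
|---|---|---|---|---|---|
| 0.5 | 0.10 | 0.98−0.87 = 0.11 | 0.96−0.73 = 0.23 | 0.98−0.88 = 0.10 | 69% → 68% |
| 0.5 | 0.25 | 0.98−0.87 = 0.11 | 0.95−0.62 = 0.33 | 1.00−0.89 = 0.11 | 68% → 62% |
| 0.5 | 0.50 | 0.98−0.87 = 0.11 | 0.93−0.54 = 0.39 | 0.98−0.94 = 0.04 | 71% → 50% |
| 1.0 | 0.10 | 0.95−0.66 = 0.29 | 0.94−0.60 = 0.34 | 0.96−0.69 = 0.27 | 76% → 73% |
| 1.0 | 0.25 | 0.94−0.65 = 0.29 | 0.93−0.56 = 0.37 | 0.96−0.74 = 0.22 | 76% → 62% |
| 1.0 | 0.50 | 0.94−0.66 = 0.28 | 0.92−0.49 = 0.43 | 0.97−0.77 = 0.20 | 77% → 47% |

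The crude difference grows in every row. The Kaplan-Meier difference shrinks or stays the same. The reason is that censoring removes patients who have just had an SBM, so those left at risk are closer to a 3-day gap, and this happens more often on naloxegol.

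**The case against.** No passage orders SBM recording to end with drug. Table 1 lists SBM documentation as routine care, so stools are charted anyway. Its columns 1 to 10 are labelled as study days and can be read as calendar days. Section 5.9 ends data collection only when consent is withdrawn. Section 12.1 calls for intention-to-treat analysis, and 12.2 makes no reference to drug. On that reading follow-up simply continues and nothing is lost. Rule 3 also needs opioid off for 24 hours or more, so an SBM alone does not stop drug, and most other rules do not depend on having had one. Time to first SBM is not cut by rule 3 at all.

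All of this stands, and it makes the harm conditional on how the site reads the documents. It does not remove the conflict between 2.1 and 12.2, nor supply the missing statement about recording.

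A reader might also infer that the loss favours naloxegol and that the log-rank test would carry this through. The calculations do not support that. The exaggeration appears in crude proportions. Section 12.2 plans Kaplan-Meier curves and a log-rank test unless everyone completes, and there censoring at drug stop tends to work against naloxegol and lowers power. Crude proportions are not excluded, however: the switch to chi-square depends on completing the study, and the plan does not say whether a patient whose drug stopped early has completed.

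**Conclusion.** The point holds as an inconsistent and incomplete definition of follow-up for the primary outcome. The two windows differ on the face of the text whenever drug is held or stopped early. Recording after drug stop is unclear, and stopping depends partly on SBMs.

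The documents do not establish that follow-up ends with drug, so no bias is shown to be built in. If a site or analyst did end it there, loss would be about 27-41% against 7-12%. The error could then run either way: about 6-11 points too large a difference with crude proportions, or a reduced difference with Kaplan-Meier. These sizes rest on assumed opioid-stop, ICU-stay and later-SBM rates. The existence of the gap does not. Because an unstated handling rule would decide the direction of the error in the primary comparison, it should be settled before the data are analysed.

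**What to change.** - **Protocol 2.1, 2.2, 2.3 and section 12.2 of protocol and SAP:** state one window. It runs from each outcome's existing start (randomization for the primary outcome) to ICU discharge, death or 10 calendar days (240 h) after randomization, whichever is first, regardless of whether study drug is held or stopped. If ICU stay is meant to be followed beyond that point, say so.
- **Table 1 and 5.9:** state that SBM time, size and Bliss score, and the other daily outcomes, are recorded to the end of that window after drug stops. Make the three SBM rows agree.
- **Section 12.2:** state that the primary outcome is not censored when study drug stops.

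The stopping rules in 5.8.1 do not change. The cost is a wording amendment and a few more days of an existing bedside form for patients still in the ICU after drug stops.

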2.2 Secondary objectives

To compare the efficacy of naloxegol (with placebo) in critically ill adults initiated on scheduled IV opioids on each of the following outcomes:

During the period from time of scheduled opioid therapy initiation (IV fentanyl equivalent dose \geq 100 mcg/day) until ICU discharge, death or 10 days of study drug administration (whatever comes first):

(Note: there are up to three days to enroll and randomize subject after the initiation of scheduled opioid therapy).

- a. Incidence of lower GI tract paralysis (\geq 3 days without a SBM)
- b. Time to first SBM (in hours)
- c. Days without a SBM
- d. Average daily opioid requirement [in IV fentanyl equivalents (mcg)].

Note:

1. For the purposes of inclusion in the study, only opioids administered by the IV route will be considered but to calculate the daily opioid requirement all opioids administered (regardless of route) will be considered. All enteral/oral opioids will be reduced by 50% when converting to the IV fentanyl equivalent.
2. Administration of opioids will be mandated by the ICU team (as per routine clinical practice based on the ICU team evaluation of regular pain assessment scores) and will not be protocolized as part of the study.
3. While IV fentanyl is the most common IV opioid used in the medical ICU at Tufts MC, other opioids (e.g. IV and oral hydromorphone, oral oxycodone) are used at times. Choice of opioid during routine patient care is currently not protocolized in the ICUs at Tufts MC and will not be protocolized as a part of this study. The choice and amount of opioid administered each day will be collected as part of the study.

During the period from time of study enrollment (i.e., randomization) to ICU discharge, death or 10 days of study drug administration (whatever comes first):

- e. Time to first SBM
- f. Daily characterization of each SBM for size (small, medium or large)
- g. Daily characterization of each SBM for consistency (using the Bliss Stool Scale)
- h. Daily characterization of use of the study laxative guidelines.
- i. Daily volume of enteral nutrition administered.
- j. % of daily enteral nutrition goal met.
- k. Daily fluid balance (i.e., 24 hr ins and outs)
- l. Daily maximal pain scale score (using nurse-administered 10 point rating scale)

Drug Substance: Movantik
 Study Number: ESR-15-11000
 Tufts IRB #12043
 Version: Protocol version #19
 Date: September 10, 2018

- m. Daily Sedation Assessment Scale (SAS) score
 - a. Average
 - b. Presence of coma (SAS = 1 or 2)
- n. Daily presence of delirium using the Intensive Care Delirium Screening Checklist (ICDSC)
 - a. Proportion of patients ever found with delirium (ICDSC \geq 4]
 - b. Days with delirium
 - c. Proportion of patients ever found with subsyndromal delirium [ICSDC = 1 to 3]
 - d. Days with subsyndromal delirium
- o. Daily total sedation administered (in midazolam equivalents)
- p. Occurrence of lower GI tract paralysis requiring consultation by a gastroenterologist or a surgeon.
- q. Days without mechanical ventilation support.
- r. Duration of ICU stay.
- s. In patients having a clinical reason for foley catheter placement, abdominal pressure measurement every 8 hours:
 - i) % patient of patients having abdominal pressure \geq 12 mmHg; ii) % patient of patients having abdominal pressure \geq 20 mmHg; iii) Average daily maximal abdominal pressure score
- t. Time from first initiation of \geq 100 fentanyl equivalents to administration of first dose of study medication.

